8.1.1 Radiological Assessment

For each participant, the same radiological method for head and neck and for chest must be used throughout the study. The schedule of collection of iv contrast-enhanced CT scan or MRI of head and neck (which cover the orbits), CT scan of the chest, and ¹⁸F-FDG-PET/scan (from the skull base to the proximal upper legs) is provided in [Table 1](#), [Table 2](#), and

[Table 3](#).

¹⁸F-FDG-PET scan is preferred to facilitate pre-and posttreatment evaluation of metabolic response and the need for posttreatment neck dissection. If physical examination and imaging suggest residual disease at the primary site at EOT, a biopsy should be performed whenever possible to confirm residual disease; otherwise, participants will undergo serial follow-up.

Additional imaging assessments may be performed at any time during the study at the Investigator's discretion to support the efficacy evaluations for a participant. Clinical progressive disease (PD) is recommended to be confirmed by imaging and/or endoscopy (i.e. biopsy).

If an off-schedule imaging assessment is performed because progression is suspected, subsequent assessments should be performed in accordance with the original imaging schedule.

Measurability of the Tumor at Baseline

At baseline, participants may be included with measurable disease or with only evaluable, non-measurable disease according to RECIST v1.1 and as assessed by the Investigator. Measurable disease is defined as the presence and selection of at least 1 measurable nodal or non-nodal lesion. The assessment of participants at baseline according to RECIST v1.1 is covered in [Appendix 2](#).

Non-measurable disease means that only non-measurable lesions exist at baseline. Guidance on how participants with only non-measurable disease at Baseline will be evaluated for complete response and progression based on RECIST v1.1 is also defined in [Appendix 2](#).

Images may be collected retrospectively from the investigational sites in case it is later determined that an independent read is appropriate.

8.1.2 Radiological/Clinical Assessment at EOT and Follow-up

All participants will be assessed at the EOT visit (20 [\pm 1] weeks) with clinical/radiological examinations as follows:

- ¹⁸F-FDG-PET or ¹⁸F-FDG-PET/CT scans for determining the overall clinical outcomes and the need for nodal dissection (¹⁸F-FDG-PET should be ordered before examination under anesthesia with endoscopy, biopsies, and tonsillectomy, to help identify potential primary sites before any intervention occurs).
- Ear, nose, and throat, and fiberoptic endoscopy.

These clinical assessments are to be performed according to the schedule presented in [Table 1](#), [Table 2](#), and

[Table 3](#).

If the EOT scan was positive AND the participant underwent salvage surgery and END, no further ¹⁸F-FDG-PET scans should be performed. If EOT results were inconclusive AND the participant did not undergo salvage surgery and END, the ¹⁸F-FDG-PET scan should be repeated 12 weeks after EOT (Week 31 ± 2 weeks).

Clinical PD must be verified by imaging and/or biopsy, wherever possible. The presence or absence of residual viable tumor cells will be determined via a histopathological examination.

Negative ¹⁸F-FDG-PET scan at Baseline, with a positive ¹⁸F-FDG-PET scan at EOT is a sign of PD based on a new lesion if considered related to the disease under study (a confirmatory biopsy should be performed whenever possible). Further details of the interpretation of ¹⁸F-FDG-PET scan in this study are supplied in [Appendix 2](#).

In case of doubt of a clinical local-regional recurrence or distant metastasis before the EOT, imaging by CT/MRI scan should be performed to verify disease progression.

During the follow-up period the participants will undergo ear, nose, and throat examination, fiberoptic endoscopy as per institutional guidelines, and MRI and/or CT as per the schedule CT as per the schedule presented in

[Table 3](#).

8.2 Safety Assessments and Procedures

The safety profile of the study intervention will be assessed through the recording, reporting, and analysis of baseline medical conditions, AEs, physical examination findings, vital signs, electrocardiograms, and laboratory tests.

Comprehensive assessment of any potential toxicity experienced by each participant will be conducted starting when the participants give informed consent and throughout the study. The Investigator will report any AEs, whether observed by the Investigator or reported by the participant; the reporting period is specified in Section [8.3](#).

8.2.1 Physical Examinations

- A complete physical examination will include, at a minimum, assessments of the brief physical examination as well as neurological systems, and will be done at screening and EOT.
- A brief physical examination will include, at a minimum, assessments of the skin, lungs, cardiovascular system, and abdomen (liver, spleen, and pancreas) as well as the head, mouth, and neck area, and will be done during treatment and follow-up visits.
- Investigators will pay special attention to clinical signs related to previous serious illnesses.

8.2.2 Vital Signs

- Blood pressure and participant's position during measurement; pulse; respiratory rate; temperature and location of measurement, weight, and height (at Screening only) will be measured and recorded.
- Blood pressure and pulse measurements will be preceded by at least 5 minutes of rest for the participant in a quiet setting without distractions (e.g. television, cell phones) and measured with an automated device. Manual techniques will be used only if an automated device is not available.

8.2.3 Electrocardiograms

- Single 12-lead ECG will be obtained as outlined in the SoA using an ECG machine that automatically measures heart rate, PR, RR, QRS, and QT. If QTcF is not automatically measured, it can be calculated separately.
- A standard single 12-lead ECG will be recorded after 10 minutes of supine rest according to the schedule shown in [Table 14](#).

Table 14 ECG Collection Plan

Study Visit or Cycle	Day	Time Relevant to Dosing
Screening	-28 to -1	NA
Cycle 1	1	predose ^a 0.5-4 hours postdose
Cycle 1	8	predose ^a 0.5-4 hours postdose

ECG=electrocardiogram, NA=not applicable.

a To be performed prior to all predose blood collection.

If several ECGs (scheduled and unscheduled) are performed during Screening, the latest results must be recorded and used.

- All ECG readings will be performed locally by the Investigator, or a cardiologist will be consulted, if clinically indicated.
- Additional ECGs can be performed if clinically indicated.

Abnormal ECG Findings

In case of **abnormal** ECG findings relevant to QT interval (e.g. QTcF prolongation > 30 ms compared to baseline, or QTcF interval > 500 ms, Torsade de Pointe, ventricular tachycardia, ventricular fibrillation, flutter) or any other new clinically significant cardiac abnormality, triplicate ECG readings will be performed including the already abnormal ECG reading. If the abnormal ECG finding is confirmed after triplicate ECG readings, the participant must be referred to a local cardiologist.

Significant QTcF prolongation is defined as an interval > 500 ms or an interval which increases by 60 ms over baseline.

Management of Participants with Significant QTcF Prolongation

If the QTcF prolongation is confirmed by **either** criterion (i.e. QTcF interval > 500 ms **or** > 60 ms increase from baseline) the following actions will be taken (see also [Table 7](#) and [Table 8](#)):

- CCI [REDACTED]
- The participant will be monitored including assessment of electrolytes in plasma (potassium, calcium, and magnesium), treated appropriately and closely followed (ECGs at least 3 times per week) until resolution to within 30 ms from baseline or QTcF < 480 ms.
- CCI [REDACTED].
- The participant will be referred to a cardiologist.
- The Medical Monitor will be consulted prior to administering further xevinapant doses.
- CCI [REDACTED]
[REDACTED]

If the prolongation is confirmed by **both** criteria (i.e. QTcF interval > 500 ms **and** > 60 ms increase from baseline) the following actions will be taken:

- CCI [REDACTED]
- The participant will be monitored including assessment of electrolytes in plasma (potassium, calcium, and magnesium), treated appropriately and closely followed (ECGs at least 3 times per week) until resolution to within 30 ms to baseline.
- CCI [REDACTED]
- The participant will be referred to a local cardiologist.

8.2.4 Clinical Safety Laboratory Tests

- Blood and urine samples will be collected for the clinical laboratory tests listed in [Appendix 8](#) at the timepoints listed in the SoA. All samples will be clearly identified.
- The following tests are only performed at Screening: coagulation, HBV, HCV, HIV tests and SARS-CoV-2 test (PCR or antigen test, if applicable). Additional coagulation tests may have to be performed according to local practice.
- Pregnancy testing (serum or highly sensitive urine, as required by local regulations) will be conducted according to the schedule in [Table 1](#), [Table 2](#), and,
- [Table 3](#).
 - Pregnancy testing (serum or highly sensitive urine, as required by local regulations) will be conducted at the end of relevant systemic exposure of the study intervention.

- Additional tests may be performed at any time during the study, as determined necessary by the Investigator or required by local regulations.
- The tests will be performed by the local laboratory. For HPV testing, see additional instructions in Section 8.2.4.1.
- The Investigator will review each laboratory report, document this review, and record any clinically significant changes occurring during the study as an AE, unless it does **not** meet the AE definition, as specified in [Appendix 7](#). The laboratory reports will be filed with the source documents.

8.2.4.1 HPV Status in Participants with OPC

- In participants with OPC, tumor HPV status should be determined by p16 IHC.
- For OPC participants, p16 expression is scored as positive if a total H- Score ≥ 210 or $\geq 70\%$ of the tumor cells with 3+ staining intensity in nucleus and cytoplasm. H-score should be calculated by the formula: $H=[\% \text{ weak (1+)} \times 1] + [\% \text{ moderate (2+)} \times 2] + [\% \text{ strong (3+)} \times 3]$.
- p16 IHC results obtained prior to the participant's consent to participation in the study are acceptable, pathological report should be available.
 - If the report is not available for HPV status by p16 IHC, for countries where EU IVD Regulation (IVDR) is applicable, only local lab testing on an **CCI** [REDACTED] is allowed.
 - For countries not falling under the EU IVD Regulation (IVDR), the assessment can be done locally **CCI** [REDACTED]. If the site is not able to perform HPV testing by p16 IHC, it will be evaluated by a central laboratory.
- The results of existing local data must be captured on the appropriate eCRF upon enrollment into the study after the participant has signed the ICF.
- For non-OPC participants, if tumor HPV status is available, this can also be captured on the eCRF as well; for these participants if no result is available, it is not needed to have the HPV status assessed.

8.2.5 Safety Monitoring Committee (SMC)

The SMC will perform a safety review after 6, 12, 18, and 38 participants have been treated for at least 5 weeks or have experienced a DLT-like event. For the SMC review after 18 participants the tolerability of treatment will be assessed using the DLT-like criteria (Section 8.2.5.1) during the initial 5 weeks for each participant (DLT-like assessment period). Additional SMC reviews may be requested by the Sponsor or SMC. In addition, the SMC will decide upon stopping of the study:

- In case of unacceptable toxicity
- In case of treatment related death without possible alternative causality.

For further details, see Section 9.2 and Appendix 5.

8.2.5.1 Definition of DLT-like Events

DLT-like events are defined as any of the following laboratory abnormalities or treatment-related AEs occurring during the DLT-like assessment period of 5 weeks that are assessed as related to study intervention:

- Asymptomatic CTCAE Grade 4 neutropenia that persists > 7 days
- CTCAE Grade ≥ 3 febrile neutropenia
- Grade 4 Thrombocytopenia without bleeding lasting ≥ 5 days or Grade ≥ 3 thrombocytopenia with bleeding or requiring platelet transfusion.
- CTCAE Grade ≥ 3 nonhematologic toxicity, including but not limited to:
 - CCI [REDACTED]
 - CTCAE Grade 4 dermal toxicity or mucositis if it interferes with study intervention delivery.
- A dose of less than 60% of the planned cumulative dose of xevinapant or cisplatin in the respective treatment cycle due to treatment-related AE occurring during the DLT-like assessment period.

Note: If dose reduction at the start of a next treatment cycle of xevinapant /cisplatin/carboplatin is required according to dose modification guidelines (Section 6.5.1.2), it is considered as a new planned dose.

- RT delay > 2 weeks due to a treatment-related AE occurring during the DLT-like assessment period
- CTCAE Grade 2 or higher ototoxicity worsening by 2 grades or more from baseline if deemed treatment limiting by the investigator
- Any occurrence of drug-induced liver injury (DILI) meeting the Hy's law criteria (i.e. defined as aminotransferases $> 3 \times$ ULN, alkaline phosphatase $< 2 \times$ ULN, total bilirubin $\geq 2 \times$ ULN, with no other reason to account for these abnormalities)
- CTCAE Grade ≥ 3 laboratory abnormalities
- Any other life-threatening toxicity
- Grade 5 toxicity

Exceptions:

1. Grade 3/4 nausea, vomiting, and diarrhea will be considered DLT-like events only if they persist for at least Grade 3 for > 3 days despite optimal therapy. Grade ≥ 3 fatigue and anorexia will not be considered DLT-like events
2. Common CRT-related Grade 3 toxicities including laryngeal inflammation, skin reaction, dysphagia, oral dysesthesia, mucositis, mucosal infection, skin infection, oropharyngeal pain, laryngitis, pharyngitis, decreased appetite, salivary duct inflammation, radiation recall reaction,

and xerostomia will not be considered DLT-like events unless if it leads to permanent discontinuation of treatment as assessed by the investigator.

3. CTCAE Grade ≥ 3 lab abnormalities that are not interfering with study intervention delivery according to investigator assessment will not be considered DLT-like events.
4. Grade ≥ 3 or higher electrolyte abnormality that lasts up to 72 hours, is not clinically complicated, and resolves spontaneously or responds to conventional medical interventions.
5. Grade 3 amylase or lipase that is not associated with symptoms or clinical manifestations of pancreatitis.
6. Amylase increases originating from the salivary gland will also not be considered DLT-like events.

The SMC will confirm any DLT-like event.

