1.3 Schedule of activities, Table 1, Table 2, and Table 3	Added weekly audiology testing prior to weekly cisplatin dosing, if clinically indicated.	As per request from health authority

Section # and Name	Description of Change	Brief Rationale
5.1 Inclusion criterion #9	To harmonize the period for contraceptive measures for chemotherapy across the protocol as per local guidelines and local product information.	As per request from health authority and IRB
5.2 Exclusion criterion #15	To change time period when a live attenuated vaccines can be used prior to start study intervention from 30 to 28 days.	To harmonize with Section 6.8.3.1 Prohibited Medications with Xevinapant
6.5.2 Chemotherapy, and 6.8.1.1 Antiemetics	Update on proposed antiemetic regimens. Dexamethasone is proposed at 8 mg for Day 1 and 4 mg for Days 2 and 3 after cisplatin infusion; aprepitant is proposed to be taken only on Days 1 and 2 after cisplatin infusion.	Alternative dosage/schedule for anti-emetic regimens are proposed to mitigate DDI risks
8.2.5 Safety Monitoring Committee	To add that the SMC can decide to stop the study in case of unacceptable toxicities or treatment related deaths.	As per request from health authority
8.2.5.1 Definition of DLT-like events	Updated the definition of DLT-like events to include Hy's law cases and Grade ≥ 3 lab abnormalities, and exceptions to the Grade ≥ 3 lab abnormalities.	As per request from health authority
8.2.7 Audiometry	To add section for audiometry testing, which is to be done prior to weekly cisplatin dosing and follow up if clinically indicated.	As per request from health authority
8.3.4 Pregnancy	Updated reporting of pregnancy information in the CRF.	Updated in line with Sponsor requirements

10 Reference list	Added new reference.	Updated to include the current reference list
Appendix 2	Update RECIST criteria to remove the recording of non-target lesions in evaluation visits.	Updated in line with study requirements
Appendix 3	Updated the section to harmonize the period for contraceptive measures for chemotherapy across the protocol as per local guidelines and local product information.	As per request from health authority and IRB
Appendix 5 Study Governance	Added paragraph on applicable regulations to protect personal data and updated the composition of SMC.	Added information to clarify follow-up if regulations to protect personal data are not followed, and to allow additional SMC members, if considered necessary

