6.5.1.2 Dose Modification, Interruption, and Discontinuation of Xevinapant Treatment

For participants who do not tolerate the study intervention, adjustments to the study intervention dose are permitted to allow the participant to continue on-study intervention according to the guidelines below.

The guidelines for xevinapant dose modifications for toxicities considered at least possibly related to study intervention are outlined in Table 7 and Table 8, for combination therapy and monotherapy, respectively. These dose modifications are recommendations unless otherwise specified as mandatory. All dose modifications should be based on the worst preceding toxicity (NCI-CTCAE v5.0). Additionally, nontreatment-related events, or unexpected toxicities may require interruption of study intervention at the discretion of the Investigator.

In case a dose reduction is necessary, the study intervention will be administered as follows:
For each participant, a maximum of 2 dose reductions of xevinapant will be allowed during the study.

The volume of the oral solution equivalent to each dose level is the following:

- Planned dose (Level 0): CCI corresponds to CCI mg/day of xevinapant
- Dose Level 1: CCI corresponds to CCI mg/day of xevinapant
- Dose Level 2: CCI corresponds to CCI mg/day of xevinapant

General rules for xevinapant administration throughout the treatment period (C1 to C6) are:

[figure not shown]
- The number of treatment days with xevinapant intake should not exceed 14 days per cycle.
- In case of tolerability issues, up to 2 sequential xevinapant dose reductions of CCI mg/day (CCI of oral solution) per step will be allowed, down to a minimum dose of CCI mg

CCI [REDACTED] of oral solution). If further dose reduction is required, the participant must be permanently discontinued from xevinapant administration (other ongoing treatments can continue, see Sections 6.5.2 and 6.5.3).

[figure not shown]
- If the onset of several toxicities leads to conflicting recommendations as described in Table 7 the most conservative dose adjustment among all toxicities presented must be followed.
- **No re-escalation** of xevinapant dose after dose reduction will be allowed during the study. Once xevinapant dose has been reduced, participant will keep receiving the same dose until the EOT, or until further dose reduction or permanent treatment discontinuation, if required due to tolerability issues.

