- Mild: A type of adverse event that is usually transient and may require only minimal treatment or therapeutic intervention. The event does not generally interfere with usual activities of daily living.
- Moderate: A type of adverse event that is usually alleviated with additional specific therapeutic intervention. The event interferes with usual activities of daily living, causing discomfort but poses no significant or permanent risk of harm to the research participant.
- Severe: A type of adverse event that interrupts usual activities of daily living, or significantly affects clinical status, or may require intensive therapeutic intervention.

Do not confuse an AE that is assessed as severe with an SAE. Severe is a category used to rate the intensity of an event; both AEs and SAEs can be assessed as severe. An event is defined as “serious” when it meets at least 1 of the predefined criteria specified in the definition of an SAE, NOT when it is rated as severe.

Investigators will reference the NCI-CTCAE, version 5.0 (publication date: 27 Nov 2017), a descriptive terminology that can be used for AE reporting.

A general grading (severity/intensity; hereafter referred to as severity) scale is provided at the beginning of the above referenced document, and specific event grades are also provided.

If the severity for an AE is not specifically graded by NCI-CTCAE, the Investigator is to use the general NCI-CTCAE definitions of Grade 1 through Grade 5, using their best medical judgment.

The 5 general grades are:

- Grade 1 or Mild
- Grade 2 or Moderate
- Grade 3 or Severe
- Grade 4 or Life-threatening
- Grade 5 or Death

Any clinical AE with severity of Grade 4 or 5 must also be reported as an SAE. However, a laboratory abnormality of Grade 4, such as anemia, or neutropenia, is considered serious only if the condition meets one of the serious criteria specified below.

If death occurs, the primary cause of death or event leading to death will be recorded and reported as an SAE. “Fatal” will be recorded as the outcome of this specific event and death will not be recorded as separate event. Only, if no cause of death can be reported (e.g. sudden death, unexplained death), the death per se might then be reported as an SAE.

Assessment of Causality

- The Investigator will assess the relationship between study intervention and each AE/SAE occurrence:

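### Could exception 3 of the DLT-like definition cancel a Grade 4 cytopenia that the same section lists as an event?

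*Protocol*

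**What the plan says.** Protocol 8.2.5.1 defines the primary endpoint as a list of criteria followed by six numbered exceptions.

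- Two criteria are purely laboratory cytopenias. One begins "Asymptomatic CTCAE Grade 4 neutropenia that persists" and requires more than 7 days. The other begins "Grade 4 Thrombocytopenia without bleeding lasting" and requires at least 5 days. Neither mentions treatment delivery.
- A separate criterion covers CTCAE Grade 3 or higher laboratory abnormalities in general.
- Exception 3 states that Grade 3 or higher "lab abnormalities that are not interfering with study intervention delivery according to investigator assessment will not be considered DLT-like events". It names no criterion.
- Two other criteria carry their own condition: Grade 4 "dermal toxicity or mucositis if it interferes with study intervention delivery", and ototoxicity "if deemed treatment limiting by the investigator".

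The summary of changes says the definition was updated to include Hy's law cases and Grade 3 or higher laboratory abnormalities, "and exceptions to the Grade ≥ 3 lab abnormalities". SAP 15.1 refers back to Protocol 8.2.5.1 and adds no rule of precedence.

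**The concern.** Nothing in the wording of exception 3 confines it to the generic laboratory criterion, and elsewhere the documents treat cytopenias as laboratory findings. Protocol Appendix 7 says "a laboratory abnormality of Grade 4, such as anemia, or neutropenia, is considered serious only if the condition meets" one of the seriousness criteria, and SAP Appendix 2 grades neutrophil and platelet counts as laboratory parameters. An investigator could therefore decide that ten days of Grade 4 neutropenia did not interfere with delivery and record no DLT-like event. Another could apply the neutropenia criterion and record one.

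This is the only primary endpoint, and the error would run one way. Under Protocol 9.3 an exempted participant who received at least 60% of planned xevinapant and cisplatin stays in the DLT analysis set as a non-event. The numerator could then be too small, which favours a finding of tolerability.

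**Working it through.** **1. The plan's own figures.** Protocol 9.2 gives 85.9% for staying below 40% at 18 participants and 83.0% for staying below it at both looks with 38, at a true rate of 30%. Exact binomial calculation gives P(X18 ≤ 7) = 0.859. The joint figure is Σ P(X18 = a)·P(X20 ≤ 15 − a) over a = 0 to 7, which is 0.830. Both reproduce. Neither uses exception 3, so the sample size and event limits do not depend on its scope.

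**2. Wording side by side.** The generic criterion and the opening of exception 3 use the same phrase, apart from *laboratory* shortened to *lab*. Neither cytopenia criterion uses that phrase. Exceptions 4 to 6 (electrolytes, amylase, lipase) continue as a run of laboratory exceptions. The summary of changes introduces the generic criterion and its exceptions together.

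**3. What each reading does to the list.** Take a Grade 4 neutropenia lasting more than 7 days.

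| Case | Broad reading of exception 3 | Narrow reading |
|---|---|---|
| Interferes with delivery | Event, already caught by the generic criterion | Event |
| Does not interfere | Not an event | Event, under the neutropenia criterion |

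Under the broad reading the neutropenia criterion never decides a case. The same holds for Grade 4 thrombocytopenia without bleeding. The broad reading would also exempt a Hy's law case whose liver values are Grade 3 or higher, although that criterion was added in the same change. The narrow reading gives every criterion an effect.

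**4. Room for the broad reading to matter.** Cisplatin is scheduled on study days 2, 9, 16, 23, 30, 37 and 44, and the assessment period is 5 weeks (days 1 to 35). Six days lie between consecutive infusions, for example days 3 to 8.

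- Neutropenia lasting more than 7 days cannot fit into six days. While cisplatin is ongoing it must cover a scheduled infusion.
- Thrombocytopenia of 5 or 6 days can fit, for example days 3 to 7.

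Covering an infusion day is not itself interference. Retreatment conditions are in Table 7, which is redacted. Section 6.5.1.2 says "All dose modifications should be based on the worst preceding toxicity", and 6.5.2.1 bases chemotherapy adjustment on the nadir counts. A prolonged Grade 4 neutropenia would thus probably affect delivery, and exception 3 would then not apply on either reading. The gap that remains is mainly short Grade 4 thrombocytopenia.

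**5. Size where an analysis remains.** SAP 7.1 keeps the 6-participant safety committee analysis. One participant is 1/6 = 16.7 points. The exact Clopper-Pearson limits are the 2.5% quantile of Beta(x, n − x + 1) and the 97.5% quantile of Beta(x + 1, n − x).

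| Events | Rate | 95% CI |
|---|---|---|
| 0/6 | 0% | 0.0 to 45.9 |
| 1/6 | 16.7% | 0.4 to 64.1 |
| 2/6 | 33.3% | 4.3 to 77.7 |

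For 0/6 the upper limit is 1 − 0.025^(1/6) = 0.459. Each interval contains most of the next one. Protocol 9.2 excludes the 40% threshold at this review, so no rule is crossed.

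**The case for a change.** The strongest case for a change is that the definition of a sole primary endpoint should not rest on inference. A summary of changes is not operative text. The safety committee confirms DLT-like events, but it applies the same unscoped wording, and nothing requires it to look at events an investigator has exempted. SAP Appendix 1 builds the committee's DLT set on the investigator's classification. SAP 14 and 16 are marked as not conducted while 15.1 is not, so a rate with its interval is still formally specified. One sentence would settle the scope.

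Three things stand: the operative text does not state the scope, any error would lower the rate, and 15.1 is formally still in place.

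Three things do not. First, it might be argued that the section writes a treatment condition into a criterion whenever it wants one, so the cytopenia criteria were meant to be unconditional. But exceptions 1, 2, 4 and 5 add conditions on duration, discontinuation or symptoms that the criteria lack, so silence in a criterion proves little. Second, the committee is not blind to exempted events: SAP Appendix 1 gives it participant profiles and plots of neutrophils and platelets over time. Third, giving a count under both readings is not free. Exempted events would have to be reclassified for relatedness and duration, and roughly weekly blood counts may not show whether a thrombocytopenia lasted 5 days.

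**Conclusion.** No change to the plan is needed. Exception 3 is loosely drafted, but its matching phrase, the amendment summary and the redundancy created by the broad reading all point to the generic laboratory criterion alone. A scoping sentence would record what a careful reader already infers.

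The effect on the endpoint is unknown and possibly nil. It is bounded at 16.7 points per reclassified participant in the 6-participant review, which is qualitative. The synoptic report list in SAP 7.1 has no DLT-like table. SAP version 2.0 (14 March 2025) also postdates the database lock of 20 September 2024, so a clarification could not alter how events were classified during the trial. If a DLT-like count is reported after all, saying which reading was used is ordinary reporting and needs no revision of the plan.

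This rests on two assumptions that cannot be checked: that redacted Table 7 holds or modifies treatment for most prolonged Grade 4 cytopenias, and that the safety committee charter, which is not among the documents, contains no contrary rule. If Table 7 did not do so, more events would depend on the scope of exception 3, but the retained analyses would still contain no decision that it could change.
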